9.0 STATISTICAL CONSIDERATIONS

9.1 Study Analysis/Statistics

This study will compare the performance of the [18F]-DCFPyL PET-CT subsystem on the RefleXion X1 system to detect selected lesions in patients with prostate cancer with the SOC diagnostic [18F]-DCFPyL PET-CT.

One key metric will be the percent of patients with lesions identified on SOC PET-CT that are not identified on X1 (false negatives if considering SOC the true standard). While patients will not have their SOC scan evaluated prior to X1, we anticipate at least 50% will have positive lesions identified on SOC in our patient population. With 12 patients with SOC detected lesions, there is at least 14% chance of finding a false negative if the true false negative rate is 15%, and 93% of observing a false negative if the true false negative rate is 20%.

For the SOC [18F]-DCFPyL PET-CT, the maximum SUV and the greatest dimension in centimeters will be recorded for each PET avid malignant lesion identified by the nuclear medicine radiologist. The

patient's radiation oncologist will interpret the X1 PET scan for the same metrics. Any discordances will be documented, and the final disposition recorded after a discussion between the radiation oncologist and the nuclear medicine radiologist.

Graphical presentations will be provided to compare SOC positive lesions and X1 positive lesions, and SOC positive lesions and X1 negative lesions with regards to lesion size, lesion location (bone, lymph nodes, soft tissue, visceral organ) and SUV uptake.

The true positive lesions identified on the X1 PET images will be identified and used for BgRT planning. For the secondary endpoint, simulated planning using the RefleXion treatment planning software will be performed, and the radiation dose to organs at risk calculated. Principal investigator will determine whether this plan is acceptable or not. The percent of cases in which RefleXion [18F]-DCFPyLcPET data led to an acceptable plan will be recorded (descriptive statistics).

Because this is an exploratory study, descriptive statistics will be utilized to quantify results. Mean, standard deviation, IQR, and range will be reported for each continuous variable. Frequency and percentage will be reported for categorical variables. Statistical significance will be assessed at the 0.05 level, one-sided.

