9.3 Sample Size, Accrual Rate and Study Duration

- **Total accrual:** We will accrue a maximum of 25 evaluable participants
- **Accrual rate:** Accrual is expected to be completed in 12 months.
- **Study duration** is expected to be about 18 months.
- **Participant duration** will be about 72 hours

This study is designed to enroll up to 25 evaluable patients, and criteria for patient selection are outlined above. This sample size was determined a priori to represent a sufficient number of patients for a pilot study to evaluate PSMA-positive lesions to describe imaging performance of the [18F]-DCFPyL PET-CT subsystem on the RefleXion X1 system across a spectrum of clinical scenarios.

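### Section 9.1 gives 14% as the chance of seeing a false negative at a true 15% rate; that is the chance of seeing none, and the correct figure is 86%

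*Combined protocol and SAP*

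**What the plan says.** Section 9.1 of the combined protocol and SAP names as a key metric "the percent of patients with lesions identified on SOC PET-CT that are not identified on X1 (false negatives if considering SOC the true standard"). The unit is the patient. The section then says "we anticipate at least 50% will have positive lesions identified on SOC in our patient population". With the limit in Section 9.3, "We will accrue a maximum of 25 evaluable participants", half of the patients is about 12.

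The operating characteristic follows in one sentence. It opens "With 12 patients with SOC detected lesions" and makes two claims:

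- "there is at least 14% chance of finding a false negative if the true false negative rate is 15" percent;
- "and 93% of observing a false negative if the true false negative rate is 20" percent.

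No other section corrects these figures or gives different ones.

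**The concern.** The two claims share one sentence, one denominator and one event, so one formula should give both. With the number of patients fixed at 12, a rise in the true rate from 15% to 20% cannot move the chance of seeing a false negative from 14% to 93%. One of the two figures must be wrong, or must describe a different event.

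This is the protocol's only quantitative statement of what the design can show, and it concerns the metric closest to the primary comparison. A reader who takes it at face value would conclude that a 15% miss rate would go unnoticed in about 86% of such pilots. The sentence also obscures the caution that the number 14% properly supports: a result of no misses in 12 patients would still be fairly common if the true rate were 15%.

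**Working it through.** **Inputs, all from Section 9.1**

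- Patients with SOC-detected lesions: n = 12.
- True false-negative rates: p = 0.15 and p = 0.20.
- Stated chances of observing a false negative: 14% (with the qualifier that it is at least this) and 93%.

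The one-sided 0.05 significance level in the same section plays no part in this calculation.

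**Formula.** If patients are independent and each SOC-positive patient is a false negative with probability p, then P(none) = (1 − p)^n and P(at least one) = 1 − (1 − p)^n.

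**Step 1: reproduce the plan's figure at 20%.** 1 − 0.80^12 = 1 − 0.0687 = 0.9313. This is the printed 93%, so the plan's method is the formula above.

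**Step 2: apply the same formula at 15%.** 1 − 0.85^12 = 1 − 0.1422 = 0.8578, or 86%. The printed figure is 14%.

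| True rate | P(none) | P(at least one) | Printed |
|---|---|---|---|
| 15% | 14.2% | 85.8% | 14% |
| 20% | 6.9% | 93.1% | 93% |

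The first printed figure comes from the P(none) column and the second from the P(at least one) column.

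**Step 3: look for another reading that gives 14% at p = 0.15.**

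- Exactly one false negative in 12: 30.1%.
- At least two: 55.6%. At least three: 26.4%. At least four: 9.2%.
- Poisson approximation with mean 12 × 0.15 = 1.8: 83.5%.
- n = 13: 87.9%. n = 25: 98.3%.
- Number of SOC-positive patients random, Binomial(25, 0.5): 1 − (1 − 0.5 × 0.15)^25 = 85.8%.

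None of these gives 14%. Of the readings tried, only P(none) matches.

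**Step 4: the size of the jump.** On the plan's own formula, the rise from p = 0.15 to p = 0.20 at n = 12 is from 85.8% to 93.1%, about 7 points. The printed rise is 93 − 14 = 79 points.

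**Step 5: the true rate for which 14% would be correct.** Solving 1 − (1 − p)^12 = 0.14 gives p = 1 − 0.86^(1/12) = 0.0125, a true rate of about 1.2%, not 15%.

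**The case against.** The arithmetic is not in dispute. The case on the other side concerns how much the error matters and how to correct it.

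- **The qualifier.** The plan says the chance is at least 14%, and 86% is indeed at least 14%, so the sentence is literally true. The qualifier may be deliberate, since 12 is derived from a minimum share of SOC-positive patients. But the lower bound at n = 12 is 86%, and more patients only raise it. Beside an exact 93% for the same n, 14% cannot be read as a deliberately loose bound. What stands is that the qualifier can stay in the corrected sentence.
- **Nothing depends on the figure.** Section 9.3 justifies 25 patients on general pilot grounds, Section 9.1 calls the analysis descriptive, and no decision rule uses false negatives. This is correct. It limits the consequences of the error but does not make the figure right.
- **The direction is conservative.** The error understates what the pilot can reveal, and an attentive reader may notice the mismatch with 93%. That is also true, but the plan should not rely on the reader to repair it.
- **The 86% depends on n = 12.** Section 5.1 and the Appendix say that patients with no PET-avid lesion do not go on to the X1 scan, and the Appendix calls them non-evaluable. Section 9.2 replaces patients with unevaluable imaging. On that reading all 25 evaluable patients would be SOC-positive. This point stands: correcting the one number leaves the denominator open.

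**Conclusion.** The figure is wrong as written. At n = 12 and a true false-negative rate of 15%, the chance of observing at least one false negative is 85.8%. The printed 14% is the complement, so the error is 85.8 − 14 = about 72 percentage points. The companion 93% is correct.

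The result assumes independent patients with a common miss probability, the patient as the unit, and the plan's own n of 12. It is not sensitive to the last of these: 14% is also wrong at n = 13, at n = 25, and with a random number of SOC-positive patients.

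The error understates the pilot's ability to reveal misses and does not affect sample size, eligibility, conduct or analysis. It should still be corrected, because it is the protocol's only probability statement about the design.

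**What to change.** Replace 14% with 86% in Section 9.1 and name the event explicitly. For example:

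> If 12 patients have SOC-detected lesions, the probability of observing one or more false negatives is at least 86% for a true rate of 15% and at least 93% for a true rate of 20%.

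Here the qualifier means that 12 is the smallest number of SOC-positive patients expected; it can be dropped if 12 is meant as the exact number. It would also help to add that no misses in 12 patients would still occur 14% of the time at a true 15% rate.

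In the same edit, reconcile the assumed 12 with Section 5.1, Section 9.2, Section 9.3 and the Appendix. If every evaluable patient is SOC-positive and n = 25, the figures are 1 − 0.85^25 = 98.3% and 1 − 0.80^25 = 99.6%.

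The correction itself costs one number in Section 9.1 and has no effect on conduct.

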5.0 STUDY PROGRAM

5.1 Study Plan

SOC [18F]-DCFPyL PET-CT

All SOC [18F]-DCFPyL PET-CT studies should be performed on the Siemens Vision 600 PET-CT machine in the Outpatient Imaging Center (OIC) in the Department of Nuclear Medicine at City of Hope, in accordance with departmental protocol. Patients who demonstrate at least one PET avid site will then have a PET-CT on the RefleXion X1 system. A PET avid site could include the prostate gland or a metastatic site. If no PET avid lesion is seen on the SOC [18F]-DCFPyL PET-CT, then the patient will not have a PET-CT on the RefleXion X1 system.

Imaging-only session on the RefleXion X1 machine

On the day of, and upon completing the standard of care (SOC) [18F]-DCFPyL PET-CT, patients will undergo an addition “imaging-only session” on the RefleXion PET-CT. Site should make every effort to start SOC [18F]-DCFPyL PET-CT scan within 60 minutes of SOC [18F]-DCFPyL injection and subsequently start X1 RMRS scan within 120 minutes post injection (Figure 1). No additional PET tracer or any other molecule will be administered, and no therapeutic radiation will be delivered in this study. See Appendix for additional details of workflow.

Post-image-acquisition transfer of anonymized image data to the Funding Support/Industry Partner will be within one week from the X1 PET scan.

BgRT Planning

Within a week after the X1 RMRS PET scan a BgRT plan will be generated using X1 RMRS-acquired [18F]-DCFPyL PET data derived from the imaging-only session. The percent of cases where X1 RMRS [18F]-DCFPyLPET data can be used to generate an acceptable BgRT plan such that dosimetric parameters for the target and the nearby normal anatomy are met based on investigator assessment will be determined.

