APPENDIX

The following describes the general workflow:

- For patients who have SOC imaging within 6 weeks prior to SOC [18F]-DCFPyL PET-CT, suspicious lesion(s) should be identified prior to [18F]-DCFPyL PET-CT.
- Upon completion of SOC [18F]-DCFPyL PET-CT, the images are loaded into the contouring system (e.g., Eclipse, MIM).
- The radiation oncologist identifies the lesion(s) on the SOC [18F]-DCFPyL PET-CT to be imaged on X1 RMRS. Ideally PET-positive lesions should be between 1-5 cm although PET-positive lesions < than 1 cm are acceptable.
- If no lesion is identified, the patient will be informed that he will not need to undergo imaging on X1 RMRS. This patient will be non-evaluable for this study.
- A basic contour of PTV and BTZ is created for each lesion identified. The PTV should be at least 1 cm in diameter. The BTZ should add 10 mm or more depending on the anticipated amount of target motion for each lesion. A dummy OAR is also created.

- Load the CT and contour(s) into X1 RMRS.
- Create an image-only plan with patient reference point (laser confirmation) (to be done by the physicist).
- Safely position the patient onto X1 table, head first, supine: as comfortable and as close to the SOC [18F]-DCFPyL PET-CT position as possible.
- A kVCT localization followed by PET acquisition is then performed on the X1 RMRS.
- Prioritize pelvic lesion(s) first, before bladder accumulates activity, and low SUV lesions first.
- Safely remove the patient from the X1 RMRS.

The estimated time for steps on the X1 RMRS is as follows:

- Loading Patient onto Couch: 5 mins
- Patient Setup: 5 - 10 mins
- Confirming Laser and Move to Scan: 3 mins
- kVCT scan: 3 - 5 mins
- Imaging-only PET scan (depending on scan length): 20 - 35 mins
- Unloading patient from couch: 5 mins
- TOTAL TIME: 40 - 65 mins

Detailed Timeline

Time Point (min)	Nuc Med Tech	CRN	Rad Onc MD	Physicists and technologists
0	Infuse of ptylafir	Notify X1, physicist and rad onc MD		
60	Scan starts	Notify X1, physicist and rad onc MD		
90	Scan ends Images moved to PACS (10-20min)	Notify X1, physicist and rad onc MD Transport patient	Scans reviewed and lesion(s) selected Contours added	
105		Patient arrives in Rad Onc		Load the CT and contour(s) into X1 RMRS.X1 system Create an image-only plan with patient reference point (laser confirmation)

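### Section 9.1 does not say whether the key false-negative percentage, the plots and the lesions used for planning rest on the X1 read before or after discussion with the reader of the reference scan

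*Combined protocol and SAP*

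**What the plan says.** Section 9.1 (Study Analysis/Statistics) sets out the measure and the reading procedure.

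- The measure: "One key metric will be the percent of patients with lesions identified on SOC PET-CT that are not identified on X1". SOC is treated as the true standard for this purpose.
- The SOC reader is the nuclear medicine radiologist, who records maximum SUV and greatest dimension for each avid malignant lesion.
- The X1 reader: the "patient's radiation oncologist will interpret the X1 PET scan for the same metrics".
- Disagreement: "Any discordances will be documented, and the final disposition recorded after a discussion between the radiation oncologist and the nuclear medicine radiologist".
- Outputs that depend on X1 status: plots of SOC-positive lesions by whether X1 was positive or negative, and the lesions carried into planning for the secondary endpoint: "The true positive lesions identified on the X1 PET images will be identified and used for BgRT planning".

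On what the X1 reader already knows, the document is not consistent. Section 9.1 describes the aim as comparing the ability to "detect selected lesions in patients with prostate cancer", and also states: "While patients will not have their SOC scan evaluated prior to X1". Section 5.1 says: "Patients who demonstrate at least one PET avid site will then have a PET-CT on the RefleXion X1 system". The Appendix says: "The radiation oncologist identifies the lesion(s) on the SOC [18F]-DCFPyL PET-CT to be imaged on X1 RMRS". It then has each of those lesions contoured before the X1 session and makes a patient with no identified lesion non-evaluable.

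**The concern.** The procedure produces two possible answers to whether X1 identified a lesion: the radiation oncologist's own read, and the result agreed with the person who read the reference scan. The plan does not choose between them. Sections 8.1, 8.2, 9.2, 9.3, 10.3, the Synopsis and the Appendix do not settle it either.

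If the agreed result is analysed, the reference reading can enter the result of the test being evaluated. The percentage then partly measures agreement reached in conversation. The same ambiguity reaches the secondary endpoint: a lesion that the X1 reader did not call, but accepted after discussion, could count as a true positive and enter BgRT planning.

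This is the one measure that section 9.1 singles out as key, and the Synopsis and section 2.1.2 present the study as groundwork for later BgRT studies. Their readers would need to know which kind of detection rate they were given.

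**Working it through.** **1. The plan's own figures for this measure.** Section 9.1 gives the chance of seeing at least one false negative among 12 SOC-positive patients. The formula is 1 − (1 − p)^12.

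- p = 20%: 1 − 0.80^12 = 93.1%. The stated 93% reproduces.
- p = 15%: 1 − 0.85^12 = 85.8%. The stated 14% does not reproduce; 0.85^12 = 14.2% is the chance of seeing none. That is a separate slip and does not bear on which read is analysed.

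**2. Direction.** Take each kind of disagreement in turn.

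| Situation before discussion | Possible outcome | Effect on misses |
|---|---|---|
| SOC-positive, X1-negative | Stays a miss | None |
| SOC-positive, X1-negative | Re-called X1-positive | One fewer |
| SOC-positive, X1-negative | SOC lesion reclassified | One fewer, and a smaller denominator if it was the patient's only SOC lesion |
| Both positive, size or SUV differs | X1 focus judged not to be the SOC lesion | One more |

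For a missed lesion the count can only stay or fall. The last row is possible because the metrics compared are SUV and dimension, so a discordance may be one of measurement. The overall direction is therefore a tendency, not a certainty.

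**3. Denominator.** Two values can be read from the document.

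- Section 5.1 and the Appendix: SOC-negative patients are not scanned on X1 and are non-evaluable, so all evaluable patients (at most 25, section 9.3) are SOC-positive. One patient is 1/25 = 4.0 points.
- Section 9.1: at least 50% SOC-positive is anticipated, and the calculation uses 12. One patient is 1/12 = 8.3 points.

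The measure counts patients, so a reversed lesion moves it only if it changes the patient's status.

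**4. Illustration.** The documents give no reversal rate, so the counts below are assumptions. The start is the plan's hypothetical 20% with n = 25: 0.20 × 25 = 5 patients. Intervals are exact (Clopper-Pearson) 95%.

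| Assumed change | Result | 95% interval |
|---|---|---|
| None | 5/25 = 20.0% | 6.8 to 40.7 |
| 1 patient reversed | 4/25 = 16.0% | 4.5 to 36.1 |
| 2 reversed | 3/25 = 12.0% | 2.5 to 31.2 |
| 3 reversed | 2/25 = 8.0% | 1.0 to 26.0 |
| 1 removed, only SOC lesion reclassified | 4/24 = 16.7% | 4.7 to 37.4 |
| 1 miss added after a size or SUV discussion | 6/25 = 24.0% | 9.4 to 45.1 |

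A shift of one patient is small against an interval that runs from 6.8% to 40.7%.

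**The case against.** The strongest reply is that section 9.1 already calls for two records. A discordance cannot be documented unless the X1 call differed from SOC, so the read before discussion probably survives and both rates could be reported. This stands. What is missing is a statement of which read is analysed and a requirement to fix it before the discussion.

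A second reply is that section 2.1.2 aims at the technical performance of the PET subsystem, not the skill of the reader. A miss corrected in discussion may have been a reading error, and a final disposition can naturally be taken as the analysed result. This stands as a reason to report the agreed result too. It does not justify reporting only a result settled with the reference reader.

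A third is that detection at chosen sites is the documented design, as the reference to selected lesions and the Appendix show. That is fair; what is asked is that the result be described that way.

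Four stronger readings are tempting, but the documents do not support them.

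- *The reported rate will be too low.* The plan does not say that the agreed result will be used, and calling that rate too low assumes that the first read is correct.
- *The X1 read is not captured.* Section 10.3 lists only scan time for the X1 session, but it does the same for the SOC scan. Its narrative includes imaging characteristics of the tumor, and the Synopsis lists image analysis for both scans.
- *The X1 reader is the person who marked the SOC lesions.* Section 9.1 and the Appendix name the same role; neither says it is the same individual.
- *The study's conclusion could flip.* There is no success threshold, and the one-sided 0.05 level in section 9.1 is attached to no test of this measure.

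**Conclusion.** The gap is real and worth closing before images are read. The plan leaves open which X1 read defines its key percentage, its plots and the lesions used for planning, and one of the two candidates is not independent of the reference. Using the agreed result would tend to lower the miss rate, with a possible exception in the other direction.

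The size is unknown. What can be stated is the step per patient in point 3 of the working; the table in point 4 rests on assumed counts and a hypothetical starting rate. The consequence is for interpretation, since the study is descriptive. A change is still justified because the choice would otherwise be open after results are seen, and settling it costs almost nothing.

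The statement in section 9.1 that SOC is not evaluated before X1 contradicts section 5.1 and the Appendix. It matters here because it decides both the denominator and whether the X1 read can be described as made without knowledge of SOC.

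**What to change.** In section 9.1:

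1. Record and lock the X1 read (lesion seen yes/no, SUVmax, size) before any discussion with the nuclear medicine radiologist, and add it to the X1 items in section 10.3.
2. Base the false-negative percentage and the X1-positive/X1-negative plots on the locked read.
3. Report the disposition after discussion beside it, because a first read includes reader error.
4. State which read defines the true-positive lesions used for BgRT planning.
5. Describe the result as detection at SOC-selected locations, not as an independent search.
6. Reconcile the statement about SOC evaluation before X1 with section 5.1 and the Appendix, and state the resulting denominator.

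The cost is wording in sections 9.1 and 10.3 and a timestamped case report form entry; no extra scan or reader is needed. The reported false-negative rate may be slightly less favourable. Locking removes the effect of the discussion but not any prior knowledge of the SOC scan, which is why item 5 is needed as well.

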8.2 Secondary Endpoint(s)

Percent of cases where X1 RMRS [18F]-DCFPyL PET data can be used to generate an acceptable BgRT plan such that dosimetric parameters for the target and the nearby normal anatomy are met based on investigator assessment.

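### Section 9.1 sets a one-sided 0.05 level with no test to use it, while the two headline percentages have no planned confidence interval

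*Combined protocol and SAP*

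**What the plan says.** Section 9.1 sets the tone of the analysis: "Because this is an exploratory study, descriptive statistics will be utilized to quantify results". Continuous variables get a mean, standard deviation, IQR and range. For the rest, "Frequency and percentage will be reported for categorical variables". The paragraph then ends: "Statistical significance will be assessed at the 0.05 level, one-sided".

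Two percentages carry the results.

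- **Patient-level misses.** Section 9.1: "One key metric will be the percent of patients with lesions identified on SOC PET-CT that are not identified on X1".
- **Planning feasibility.** Section 8.2: "Percent of cases where X1 RMRS [18F]-DCFPyL PET data can be used to generate an acceptable BgRT plan". Section 9.1 assigns this descriptive statistics only.

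Two further statements affect what is counted. The Appendix says "The radiation oncologist identifies the lesion(s) on the SOC [18F]-DCFPyL PET-CT to be imaged on X1 RMRS", so lesions are chosen before the X1 scan. Section 9.1 says "The true positive lesions identified on the X1 PET images will be identified and used for BgRT planning", so lesions that X1 misses are not planned.

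On sample size, Section 9.3 caps accrual at 25 evaluable patients and says "This sample size was determined a priori to represent a sufficient number of patients for a pilot study". It gives neither a power target nor a precision target.

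**The concern.** A one-sided significance level needs a parameter, a null value and a direction. Sections 1, 8 and 9 supply none, so a reader cannot tell which result would be called significant, or against what. If the sentence stays, someone could choose the null after seeing the data.

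Meanwhile the results that this pilot can properly deliver, two proportions from at most 25 patients, have no planned measure of uncertainty. A report of no missed patients is easy to over-read at this size, and the study is meant to underpin later work on [18F]-DCFPyL-guided planning and delivery.

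An interval also needs a settled numerator and denominator, and the plan leaves both partly open. It does not say whether missing one of several lesions makes a patient a miss. Nor does it say whether a planning case is a patient or a lesion, or whether patients with nothing to plan remain in the denominator.

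**Working it through.** **1. The plan's own operating figures.** Section 9.1 gives the chance of seeing at least one miss in 12 SOC-positive patients, which is 1 - (1 - p)^12.

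- p = 0.20: 1 - 0.80^12 = 1 - 0.069 = 0.931. The stated 93% reproduces.
- p = 0.15: 1 - 0.85^12 = 1 - 0.142 = 0.858. The stated 14% does not reproduce; it equals the chance of seeing no miss. That is a separate error, and nothing below depends on it.

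These are detection probabilities. They involve no rejection rule and do not use the 0.05 level.

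**2. Can the 0.05 level be applied?** Only by borrowing a null. Purely as an illustration, take 15% or 20% as the null miss rate and test for a lower rate:

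| Result | p against 15% | p against 20% |
|---|---|---|
| 0/12 | 0.85^12 = 0.142 | 0.80^12 = 0.069 |
| 0/25 | 0.85^25 = 0.017 | 0.80^25 = 0.004 |
| 1/25 | 0.093 | 0.027 |

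Whether a result is significant depends on a null, and on an n, that the plan has not fixed.

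**3. Which n?** Section 9.1 works with 12 SOC-positive patients, expecting at least half of patients to be positive. Section 5.1 and the Appendix send only patients with an avid lesion to X1, and the Appendix calls the others non-evaluable. On that reading every evaluable patient is SOC-positive, up to the 25 in Section 9.3. Both values are shown.

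**4. Exact (Clopper-Pearson) two-sided 95% intervals.** With zero misses the upper limit is 1 - 0.025^(1/n). With every plan acceptable the lower limit is 0.025^(1/n). Other counts use beta quantiles. The counts are illustrations.

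| Result | n = 25 | n = 12 |
|---|---|---|
| 0 misses | 0-13.7% | 0-26.5% |
| 1 miss | 0.1-20.4% | 0.2-38.5% |
| All plans acceptable | 86.3-100% | 73.5-100% |

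**5. Effect of the planning denominator.** Suppose 25 SOC-positive patients are imaged and two have no plan, because X1 missed their lesion or the data cannot support a plan. If they stay in, the result is 23/25 = 92%, interval 74.0-99.0%. If they drop out, it is 23/23 = 100%, with lower limit 0.025^(1/23) = 85.2%. Replacing patients with unevaluable imaging (Sections 5.3.1 and 9.2) can push the percentage the same way.

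**The case against.** The strongest reply is that little hangs on this. The significance sentence is attached to no go/no-go rule, power claim or sample-size calculation, and a descriptive pilot needs no test. That stands, and it is why deletion is the first option.

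Second, frequencies will be reported, so any reader can derive an exact interval, and silence does not forbid one. Section 9.1 also offers some help in reading zero misses through its 93% figure. This stands in part: the information is not lost, but neither it nor the detection probability replaces a planned interval around the estimate.

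Third, the definitions are not wholly absent. Section 9.1 confines the comparison to selected lesions. Section 5.1 says that a plan will be generated after the X1 scan, which favours all imaged patients as the denominator. That is fair, but restricting planning to X1 true positives pulls the other way, and the choice between patient and lesion remains open.

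A reader might infer that 15% and 20% are the nulls, and so that 12 patients could never reach significance. The documents do not support this: the rates appear only as scenarios for seeing a miss. A reader might also take 26.5% as the study's precision. Section 5.1 and the Appendix point to up to 25 SOC-positive patients, for whom the limit is about half that.

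**Conclusion.** The point holds as a minor correction. The one-sided 0.05 rule cannot be applied as written, and the plan provides no interval for either headline percentage. With zero misses, the unreported uncertainty reaches a true miss rate of 13.7% at n = 25, or 26.5% at n = 12.

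The point does not show that the analysis is invalid or that a wrong decision would follow, though a reader might infer either. The plan declares itself exploratory, and no decision or sample size uses the 0.05 level.

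The intervals assume one yes/no result per patient, independence between patients, and an n of 12 or 25. A lesion-level rate would need an interval that allows for several lesions in one patient.

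**What to change.** **Section 9.1**

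- Delete the significance sentence. If a test is intended, name its parameter, null value, direction and method instead.
- Report both percentages with exact (Clopper-Pearson) two-sided 95% confidence intervals.
- Before the first read, fix the unit as the patient and the denominator as all SOC-positive patients imaged on X1. State whether one missed lesion among several makes a patient a miss; counting any selected lesion that X1 missed would match the planning rule below.
- For the planning endpoint, count as not acceptable any patient with a selected lesion that X1 missed, or with X1 data that cannot support a plan. Keep such patients in the denominator even if they are replaced for accrual.
- Show lesion-level counts beside both percentages.

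**Section 9.3**

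- Reconcile the number of SOC-positive patients with Sections 5.1 and 9.1 and the Appendix. Then add one precision statement for that number: zero misses gives 0-13.7% if n = 25, or 0-26.5% if n = 12.

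**Cost.** Wording and minimal programming, with no added patients, scans or procedures. The downside is that wide intervals are shown openly and the acceptable-plan percentage may be lower. The lesion-level counts keep one miss among several lesions in proportion.
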